2.3.3.4 Use of Patient Diaries During the Study (Days 1-14)

During the study, participants or their care givers will record information in the patient diary on when the shampoo was used. They will also record any adverse events at the time of occurrence.

2.3.3.5 Final Follow up Assessment (Day 14, +1 day).

At the end of the 14 day follow up period, the investigator will conduct the final assessment, unless the participant is withdrawn sooner, i.e. they choose to withdraw or are withdrawn on safety grounds. At the final assessment, all participants' hair will be combed with the head louse detection comb and any lice found will be taped (with clear tape) into the participant's CRF. If any participants, or non-participating household members, have live lice at the end of the study they will be offered a standard of care treatment (Vamousse Treatment Mousse).

All adverse events and changes in concomitant medication at any point during the study will be recorded in the CRF. Patient diaries will be collected.

Any remaining supply of investigational product will be collected by the investigator.

The Completion/Withdrawal Form will then be completed.

2.3.3.6 Assessment Analysis

Any lice fixed into the CRF during the course of the study will be examined under the microscope to establish the sex and/or stage of development of the insects. It is expected that if lice are found during the monitoring period, and the product was

initially successful in eliminating the infestation, they are likely to be adult or third stage nymphs that have newly migrated to the head. The presence of small lice (nymphs) will be evidence that louse eggs had not been sufficiently affected by the treatment regimen and were not prevented from developing to the point of hatching. All CRF pages bearing lice will be archived along with the other CRF documents, the lice fixed with tape constituting a permanent record, in much the same manner as a microscope slide.

2.3.4 Concomitant Medication

The participant should not use any other form of pediculicide or physical treatment, including lice combing, for head lice while taking part in the study. If the use of such treatment occurs, the participant will be withdrawn from the study. Participants will also be instructed not to use other hair care products, such as conditioners, hair gels and sprays for the duration of the study.

Other medication can be prescribed in the normal way although participants requiring Co-Trimoxazole or Trimethoprim should also be withdrawn from the study.

All concomitant medicines should be listed in the CRF and any changes to such medicines, during the course of the study, recorded.

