2.3.7 Withdrawals

Participants may be withdrawn from the study at any time for the following reasons:

Adverse Event:

The participant is withdrawn from the study by the Investigator because of an adverse event, whether or not the Investigator believes it to be serious or caused by the study medication, and provided that the Investigator considers it is in the participant's best interest to be withdrawn. There must be a corresponding entry on the Adverse Events and/or the Serious Adverse Events Form in this instance.

Non-compliance:

The participant is withdrawn because of failure to comply with the treatment regimen, or comply with the investigations as required, but is still accessible to the Investigator.

Drop Out:

The participant withdraws consent to continue in the study, but the Investigator would otherwise consider it appropriate for him/her to continue. The participant remains accessible to the Investigator.

Lost to Follow-up:

The participant, without explanation, fails to keep appointments as scheduled for study assessments and is not seen again despite the Investigator's effort (letter, telephone, home visit etc.) to re-establish contact.

Death:

All deaths will be treated as Serious Adverse Events and Alliance Pharmaceuticals Ltd. must be informed within 24 hours. All associated documentation must be completed within 3 working days. Full details will be required including a post-mortem examination if possible.

Lack of Efficacy:

The participant elects to withdraw because the medication is not adequately effective.

Data from all participants will be collected and missing data will be imputed as described in section 3.4.

3. Analysis and Reports

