3.2 Definition of Populations to be analysed

The Per-protocol Population:

Includes all randomised participants who complete the study and are treated and followed up strictly according to the study protocol. For the purposes of the per protocol analysis, a study participant will be deemed to be non-compliant if the shampoo is not applied for at least seven (7) days during the study period and/or is not applied for four (4) consecutive days.

"Intention-to-treat" Population:

Includes all participants who consented and were treated at least once. Premature terminations due to drop out, treatment failure, adverse events etc., are included.

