Starting from a default value of 30 families per group the following results were found:

Kruskal Wallis Analysis of Data Study Size calculations based upon 5000 replicates

Normal Distribution. Test of Mean2 - Mean1 (Std.Dev. known). 2-sided . Wilcoxon-Mann-Whitney Use Truncated Normal Distribution - x < 0 -> 0, x > 1 -> 1Stratify data, (Fry-Lee Test). Two strata vars, 1:prob of strata level 2 = 0.7 2:prob of strata level 2 = 0.5Sample Size 1 as a function of Power and Significance Level. H0: Mean 2 - Mean 1=0 H1: Mean 1=0.7 H1: Mean 2=0.4 Std.Deviation 1=0.367 Std.Deviation 2=0.367, Sample Size 2 / Sample Size 1=1

Significance Level

| - 9 | | | |
|--------|------------|--------|-------|
| Number | .001 | 0.01 | 0.05 |
| Pov | ver Requir | ed: 90 | |
| 30 | 19.24 | 49.50 | 74.86 |
| 31 | 22.46 | 52.30 | 76.48 |
| 32 | 23.66 | 55.14 | 78.36 |
| 33 | 25.38 | 56.24 | 79.72 |
| 34 | 28.10 | 58.80 | 81.88 |
| 35 | 29.62 | 61.04 | 82.66 |
| 36 | 30.62 | 62.12 | 83.74 |
| 37 | 34.30 | 65.80 | 85.58 |
| 38 | 36.32 | 66.50 | 85.74 |
| 39 | 38.36 | 68.88 | 87.64 |
| 40 | 39.66 | 70.90 | 88.74 |
| 41 | 41.42 | 72.34 | 89.68 |
| 42 | 44.18 | 74.44 | 90.56 |
| | | | |

Thus 42 families per group should be sufficient to give a 90% power to detect a difference at two-sided significance level of 5%. Experience from previous studies of this kind suggests that drop-outs are infrequent. As described in section 3.2, non-compliant households will be included in the ITT analysis with the last observation for drop outs or lost to follow up cases carried forward for analysis. Nevertheless, should any families drop out of the study, recruitment will continue until at least 84 families have completed the study.

References

Analytical methods

Analyses will be conducted based on both the "intention-to-treat" and the "per-protocol" populations and will initially use conventional analytical methods employed in earlier studies. Differences between the groups in baseline characteristics, safety, acceptability, and efficacy will be tested using Fisher's Exact test for yes/no variables and the Mann-Whitney U test for ranked variables. Where analysis shows important differences in baseline characteristics between the groups, Chi-Square and rank tests stratified for these characteristics may also be conducted.

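### The protocol conflicts with itself on whether a participant withdrawn for using another lice treatment or comb is still combed on Day 14; if not, the primary outcome is lost informatively and LOCF cannot replace it for most household members

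*Protocol*

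**What the plan says.** - **Section 2.3.4** bars any other pediculicide or physical treatment, lice combing included, and continues: "If the use of such treatment occurs, the participant will be withdrawn from the study". The withdrawal is mandatory, and it is from the study, not just from the shampoo or the per-protocol set.
- **Section 2.3.3.5** on the Day 14 combing: "the investigator will conduct the final assessment, unless the participant is withdrawn sooner, i.e. they choose to withdraw or are withdrawn on safety grounds".
- **Section 2.3.7** opens permissively: "Participants may be withdrawn from the study at any time for the following reasons". Non-compliance is one listed reason, and such a person is described as still accessible. The section ends: "Data from all participants will be collected and missing data will be imputed as described in section 3.4".
- **Section 3.2** on the intention-to-treat (ITT) set: "Premature terminations due to drop out, treatment failure, adverse events etc., are included".
- **Section 3.4** holds the only imputation rule: "non-compliant households will be included in the ITT analysis with the last observation for drop outs or lost to follow up cases carried forward".
- **Sections 1.1 and 1.4**: household members who are neither index cases nor complaining are not checked for lice on Day 0, and only index cases have a scheduled check (Day 3, and Day 6 if needed) before Day 14. Anyone who reports infestation during the study is to be examined by the team and recorded as a treatment failure.
- **Section 3.1.2**: the primary outcome is the proportion of each household with active infestation at Day 14.

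**The concern.** Suspected lice are an obvious reason to buy a lice product or pick up a lice comb. That is an inference, not a statement in the protocol, but it fits the planning assumption of about 0.7 infestation in untreated families against 0.4 in treated ones. A withdrawal triggered by that behaviour is then related to the outcome and possibly to the arm. If withdrawal also ends outcome collection, the primary endpoint has informative missing values that the team could have avoided, since it visits the household on Day 14 anyway. Staff who follow section 2.3.4 with the opening clause of section 2.3.3.5 would not comb such a person. Staff who follow the end of section 2.3.7 would. Handling could differ between households in the same trial.

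**Working it through.** **Side by side: is a participant withdrawn for self-treatment combed on Day 14?**

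| Section | Answer it gives |
|---|---|
| 2.3.4 | Withdrawn from the study; silent on combing |
| 2.3.3.5, main clause | No, if withdrawn sooner |
| 2.3.3.5, explanatory clause | Yes, since self-treatment is neither own choice to leave nor a safety ground |
| 2.3.7, last sentence | Yes, data are collected from everyone |
| 3.2 | Stays in ITT, but this supplies no outcome |
| 3.4 | LOCF, for drop-outs and losses to follow-up only |

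**Can LOCF fill the gap?** For an index case the last value is the Day 0 infestation or a Day 3 or Day 6 result. For a member who was neither an index case nor complaining there is no earlier assessment, so there is nothing to carry forward. Section 2.3.7 also defines drop-out as withdrawn consent, so on a literal reading LOCF is not assigned to a self-treater at all.

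**The plan's own figure.** Inputs from section 3.4: normal rates with means 0.7 and 0.4 and SD 0.367, clipped to 0–1; two stratum variables (0.7 and 0.5); 42 families per arm; two-sided 5%. An unweighted stratified rank-sum test with 5000 replicates gives 90.5% power, against 90.56% stated. At 36 per arm it gives 85.7% (stated 83.74%) and at 30 per arm 78.5% (stated 74.86%). The planned size is not in question here.

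**Illustration of loss (assumed rates).** 10% of all control members and 4% of all treated members are infested and lost.
- As a share of infested members: 0.10/0.70 = 14.3% and 0.04/0.40 = 10%.
- Scored not infested: 0.70 − 0.10 = 0.60 and 0.40 − 0.04 = 0.36, difference 0.24.
- Dropped from the denominator: 0.60/0.90 = 0.667 and 0.36/0.96 = 0.375, difference 0.292.

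Power was simulated at member level: beta-binomial households, intra-household correlation 0.47, 42 per arm, 5000 runs, simulation error about 0.6 points. For households of 4 this correlation matches the protocol's SD: √(0.21 × (1 + 3 × 0.47)/4) = 0.356 and √(0.24 × (1 + 3 × 0.47)/4) = 0.380, average 0.368.

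| Household size, stratum weights | No loss | Scored not infested | Dropped |
|---|---|---|---|
| 4, unweighted | 91.6% | 80.6% | 90.0% |
| 4, van Elteren | 93.6% | 83.8% | 92.5% |
| 5, unweighted | 93.2% | 84.4% | 92.0% |
| 5, van Elteren | 95.2% | 87.6% | 94.0% |

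The fall is 8 to 11 points if scored not infested and 1 to 2 points if dropped. If household rates instead come from the protocol's clipped normal distribution, with member-level sampling added, the true difference is only about 0.244. Power without loss is then 81% to 86%, and the falls are 13 to 15 and about 3 points.

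**Other loss patterns** (clipped normal, households of 4, van Elteren weights, loss as a share of infested members, control/treated; 84% power without loss):
- 20%/20%: 76% scored not infested, 83% dropped.
- 20%/10%: 53% and 79%.
- No true effect (0.7 in both arms), 20%/20%: type I error 5.3% and 4.3%.
- No true effect, 10%/20%: type I error 15.6% scored not infested, nearly all favouring the test shampoo (14% to 17% across the models and weightings tried), and 5.4% dropped.

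**The case against.** A reader might infer that everyone who self-treats or does not comply goes uncombed, that their outcome is deliberately not collected, and that the ITT analysis is broken. The documents do not support this.

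- The exception in section 2.3.3.5 is explained by own choice or safety grounds only, and section 2.3.7 says data from all participants will be collected. Non-combing is one side of a contradiction, not an instruction.
- Withdrawal for non-compliance is optional, and section 3.4 keeps non-compliant households in ITT. Shampoo non-compliance is already a per-protocol matter in section 3.2.
- Leaving for lack of efficacy is the participant's own election, not a rule imposed by the plan.
- Someone who suspects lice is meant to contact the team, and infestation confirmed that way already counts as failure (section 1.4).
- Section 3.4 calls drop-outs infrequent. Nothing says lost members are scored not infested or removed from the denominator.
- More loss in the control arm would dilute the effect, which is conservative for a superiority claim.

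All of this stands, and it narrows the point to people who self-treat without first reporting. It does not remove the point: the withdrawal in section 2.3.4 is mandatory, the sections give opposite answers on combing, and keeping a person in ITT does not supply a Day 14 status.

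**Conclusion.** The concern holds as a contradiction to be reconciled. Sections 2.3.3.5, 2.3.4, 2.3.7 and 3.4 do not agree on whether a participant withdrawn for a prohibited treatment still yields a Day 14 outcome. If not, the loss is plausibly informative and LOCF cannot repair it for most non-index members.

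The size is unknown because the protocol gives no rate. Under the assumed 10%/4% loss, power falls by roughly 8 to 11 points if lost members are scored not infested, somewhat more with clipped normal household rates, and by 1 to 3 points or so if they are dropped. Equal loss leaves type I error near 5%; inflation needs more loss in the treated arm together with scoring as not infested. These results assume that lost members would have been infested on Day 14. It should be corrected, but it does not invalidate the ITT analysis.

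**What to change.** Reconcile the four sections so that leaving the regimen and leaving follow-up are separate events:

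1. **2.3.4 and 2.3.7**: use of a prohibited treatment, or non-compliance, is recorded and affects per-protocol status only. It does not end outcome collection.
2. **2.3.3.5**: everyone still consenting and accessible is combed at the Day 14 household visit, whatever they used or missed.
3. **1.4**: live lice confirmed by the team before Day 14 remain a failure, as now. State that this carries into the primary outcome.
4. **3.4**: replace LOCF with a stated scoring rule for members with no earlier observation, the same in both arms, and report the alternative scorings as sensitivity analyses. Only withdrawn consent or loss to follow-up should give a missing outcome.

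Combing cannot reveal an infestation already cleared by self-treatment, so the number of self-treaters should be reported by arm.

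The cost is about one sentence per section and a few extra combings at a visit already planned, where non-participants found infested are already offered treatment. The prohibition itself, the treatment rules and the 42 families per arm are unchanged.

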2.3.5 Adverse Events

Space will be provided in the CRF specifically for recording observed and reported adverse events. All unwanted effects, whether considered to be caused by the study medication or not, will be reported to Alliance Pharmaceuticals Ltd. by completing the Adverse Event form.

Where an adverse event occurs, it will be recorded by the member of the study team to whom it was first notified and discussed with the CI to evaluate for seriousness, causality, and expectedness. Adverse events considered to be related to any of the study interventions will be referred to the study Local Medical Contact for review prior to any notification to the Sponsor. Commonplace childhood complaint and accidents will be included in any adverse event reviewing.

2.3.6 Serious Adverse Events

If the adverse event is serious, it shall be reported immediately, by e-mail and telephone to the Medical Contact and Alliance Pharmaceuticals Ltd. A full written report will be forwarded to Alliance Pharmaceuticals Ltd. within 3 working days.

Serious adverse events are defined as events that are fatal, life threatening, disabling or incapacitating, cause or prolong hospitalisation, overdose (of any kind, with or without symptoms), newly diagnosed cancer or clinically abnormal laboratory values (with or without symptoms).

The contacts for all serious adverse events are as set out below:

Study Sponsor contact:

[name], Qualified Person for Pharmacovigilance

Alliance Pharmaceuticals Limited

[name]

[name]

[name]

[name]

[contact]

Email: [contact]

Local Medical contact:

[name]

[name],

[name].

[name],

[name]

[contact]

Email: [contact]

2.3.7 Withdrawals

Participants may be withdrawn from the study at any time for the following reasons:

Adverse Event:

The participant is withdrawn from the study by the Investigator because of an adverse event, whether or not the Investigator believes it to be serious or caused by the study medication, and provided that the Investigator considers it is in the participant's best interest to be withdrawn. There must be a corresponding entry on the Adverse Events and/or the Serious Adverse Events Form in this instance.

Non-compliance:

The participant is withdrawn because of failure to comply with the treatment regimen, or comply with the investigations as required, but is still accessible to the Investigator.

Drop Out:

The participant withdraws consent to continue in the study, but the Investigator would otherwise consider it appropriate for him/her to continue. The participant remains accessible to the Investigator.

Lost to Follow-up:

The participant, without explanation, fails to keep appointments as scheduled for study assessments and is not seen again despite the Investigator's effort (letter, telephone, home visit etc.) to re-establish contact.

Death:

All deaths will be treated as Serious Adverse Events and Alliance Pharmaceuticals Ltd. must be informed within 24 hours. All associated documentation must be completed within 3 working days. Full details will be required including a post-mortem examination if possible.

Lack of Efficacy:

The participant elects to withdraw because the medication is not adequately effective.

Data from all participants will be collected and missing data will be imputed as described in section 3.4.

3. Analysis and Reports

3.1 Definition of End Points

3.1.1 Safety

Participants will be observed and all untoward effects will be recorded, whether or not they are thought to be related to the study treatment.

Details of the recording of adverse events are shown in section 2.3.5 and 2.3.6.

3.1.2 Efficacy

The primary outcome of the study is the proportion of individuals in each household with active head lice infestation at day 14.

Secondary objectives are:

To demonstrate the safety of Vamousse Lice Defence Shampoo in clinical use.

To demonstrate the acceptability of Vamousse Lice Defence Shampoo in daily use.

3.2 Definition of Populations to be analysed

The Per-protocol Population:

Includes all randomised participants who complete the study and are treated and followed up strictly according to the study protocol. For the purposes of the per protocol analysis, a study participant will be deemed to be non-compliant if the shampoo is not applied for at least seven (7) days during the study period and/or is not applied for four (4) consecutive days.

"Intention-to-treat" Population:

Includes all participants who consented and were treated at least once. Premature terminations due to drop out, treatment failure, adverse events etc., are included.

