Index cases will be treated with Vamousse Treatment Mousse at Day 0. A member of the MEC study team will apply the treatment. This treatment is designed to eliminate infestation. Combing to remove lice or louse eggs, in addition to the shampoo treatment, will not be given in this study.

Starting on Day 0 and ending on Day 14, all participants will commence using the shampoo as part of their daily routine. As appropriate, reminders can be issued by SMS text.

The index case will be assessed for active infestation on Day 3 ± 1 . If live lice are present, Vamousse Treatment Mousse will be applied again. Index cases with active infestation on Day 3 will be screened again on Day 6 ± 1 and re-treated if live lice are detected.

On day 14 \pm 1, all participants will be assessed for infestation by dry detection combing. Those with signs of an active infestation will be recorded as treatment failures. Anyone who has a head louse infestation at the end of the study will be provided with the standard of care treatment (Vamousse Treatment Mousse), as will any infested household member who is a non-participant.

It is possible that a participant may complain of infestation during the course of the study, although participants should be discouraged from taking active steps to detect the presence of lice. If this does occur, the individual should contact the MEC study team, who will confirm the presence of live lice and offer treatment. The individual will be recorded as a treatment failure in the CRF.

All adverse events will be monitored during the study (see sections 2.3.5 and 2.3.6) and all changes in concomitant health conditions and/or medication will be recorded (see section 2.3.4). A Completion/Withdrawal Form will be completed at the end of the study period.

2. Materials and Methods

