3.3 Proposed Primary and Secondary Analyses

- 1. To compare the efficacy of Vamousse Lice Defence Shampoo with that of The Control Shampoo and to test for superiority in the intention-to-treat population.
- 2. To compare Vamousse Lice Defence Shampoo with The Control Shampoo in terms of safety.
- 3. To compare the cosmetic acceptability of Vamousse Lice Defence Shampoo with The Control Shampoo.
- 4. To compare the efficacy of Vamousse Lice Defence Shampoo with that of the Control Shampoo in the per-protocol population.

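### The completers-only per-protocol set drops participants who leave because the shampoo failed; this affects a secondary comparison only and is minor

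*Protocol*

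**What the plan says.** Protocol section 3.2 sets two populations.

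- **Per-protocol:** "Includes all randomised participants who complete the study and are treated and followed up strictly according to the study protocol". A participant is also non-compliant below a stated amount of shampoo use. No exception is made for people who stop because of infestation.
- **Intention-to-treat:** all who consented and were treated at least once, and "Premature terminations due to drop out, treatment failure, adverse events etc., are included".

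Two routes out of the study can be linked to the outcome. Section 2.3.7 gives lack of efficacy as a withdrawal reason: "The participant elects to withdraw because the medication is not adequately effective". Section 2.3.4 bars other lice treatments and lice combing: "If the use of such treatment occurs, the participant will be withdrawn from the study".

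A third situation is different. Under section 1.4, a participant who complains of infestation during the study is checked and offered treatment. "The individual will be recorded as a treatment failure in the CRF". The section does not say that this person is withdrawn.

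The endpoint is defined at household level: "The primary outcome of the study is the proportion of individuals in each household with active head lice infestation at day 14" (section 3.1.2). Section 3.3 uses intention-to-treat for the main comparison, "to test for superiority in the intention-to-treat population", and lists the per-protocol comparison fourth: "To compare the efficacy of Vamousse Lice Defence Shampoo with that of the Control Shampoo in the per-protocol population".

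**The concern.** The endpoint is infestation, and one way to leave the per-protocol set is to leave the study because of infestation. For those people, membership depends on the outcome being compared. Each such departure takes an event out of the numerator and a person out of the denominator, so the per-protocol rate falls in whichever arm it occurs. If failures leave at different rates in the two arms, the difference between arms shifts as well, in either direction.

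What is at stake is the reading of the fourth listed comparison. A per-protocol result is useful as a check on the intention-to-treat result. If the two disagree, a reader needs to know that the gap is not produced by discarding events.

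There is also a question of unit. Section 3.2 defines membership and compliance per participant, while section 3.4 refers to non-compliant households and cites 3.2 for them. Nothing in the protocol says whether a household that loses some members from the set keeps its full denominator.

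**Working it through.** **1. The plan's own figure.** Section 3.4 gives 90.56% power with 42 families per group. I drew rates from Normal(0.7, 0.367) and Normal(0.4, 0.367) and truncated them to 0–1. I added two random binary strata (probabilities 0.5 and 0.7) and used a stratified rank test that sums within-stratum rank sums without weights. With 5,000 replicates this gives 90.9%. The figure reproduces. It is not a per-protocol calculation, so this point leaves it untouched.

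**2. Who is removed.**

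| Situation | Completes? | In the per-protocol set under 3.2? |
|---|---|---|
| Infestation confirmed mid-study, stays to Day 14 (1.4) | Yes | Not removed by the completion rule |
| Withdraws for lack of efficacy (2.3.7) | No | Removed |
| Infestation confirmed, then withdrawn for own lice treatment (2.3.4) | No | Removed |

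**3. Effect on a pooled rate.** Let p be the true infestation rate and f the share of infested participants who leave. The rate among those left is p(1 − f)/(1 − pf). The protocol gives no f, so these values are assumptions.

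- f = 10% in both arms: 0.63/0.93 = 0.677 and 0.36/0.96 = 0.375; difference 0.302 against a true 0.300.
- f = 30% control, 10% test: 0.49/0.79 = 0.620 and 0.375; difference 0.245.
- f = 10% control, 20% test: 0.677 and 0.32/0.92 = 0.348; difference 0.330.

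Equal leaving lowers both rates and barely moves the difference. Unequal leaving moves it either way.

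**4. Effect on the household endpoint.** Assumptions: 4 participants per household, beta-binomial counts, 42 households per arm, unstratified Mann-Whitney test, two-sided 5%. The within-household correlation ρ is set so that the observed proportion has SD 0.367: p(1 − p)/4 × (1 + 3ρ) = 0.367². This gives ρ = 0.52 at p = 0.7 and 0.41 at p = 0.4. Infested members are deleted with probability f, and empty households are dropped.

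| True rates, control/test | f, control/test | Mean proportion, control/test | Tests rejecting |
|---|---|---|---|
| 0.70/0.40 | 0/0 | 0.70/0.40 | about 95–96% |
| 0.70/0.40 | 5%/5% | 0.69/0.39 | about 95–96% |
| 0.70/0.40 | 10%/10% | 0.69/0.39 | about 95% |
| 0.70/0.40 | 30%/10% | 0.66/0.39 | about 90% |
| 0.55/0.55 | 0/0 | – | about 5% |
| 0.55/0.55 | 10%/30% | – | about 7–8%, mostly favouring test |
| 0.55/0.55 | 50%/20% (stress test) | – | about 13–16%, nearly all favouring control |

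The household means move less than the pooled rates in step 3 because a fully infested household that loses some members still scores 1.

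**5. Sensitivity to the model.** As a variant, I drew household rates as section 3.4 does, sampled four members from each and used a stratified test (van Elteren weights). At 10%/10%, power is 85% with or without the deletion. At 30%/10% it falls from 84% to 68%. Equal low leaving is still harmless, but the cost of unequal leaving depends on the model.

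**6. How large f can be.** Section 3.4 calls drop-outs infrequent. With 70% infested, f = 10% means 7% of control participants leave for this reason, f = 30% means 21% and f = 50% means 35%. Only the first sits comfortably with the protocol's expectation.

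**The case against.** The strongest defence is that little depends on this set. Superiority is tested in the intention-to-treat population, which expressly keeps terminations for treatment failure, and no power is claimed for the per-protocol comparison. This stands and sets the severity.

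A reader might infer that every mid-study failure disappears from the per-protocol set. The protocol does not say so: section 1.4 records such a participant as a failure without withdrawing them. Nor is every withdrawal under section 2.3.4 an event, since someone may self-treat on suspicion alone.

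A reader might also infer false claims of superiority from the 50%/20% row. That scenario conflicts with the expectation of few drop-outs, and its rejections almost all favour the control shampoo. The study is double-blind, and the protocol gives no ground for such a split between equally effective products.

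On the household unit, it is tempting to say that a household with three infested leavers and one clean completer scores 0 out of 1. A literal reading allows it. But section 3.4 also speaks of compliance by household, and the protocol does not settle the denominator.

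Finally, any per-protocol set conditions on events after randomisation, and a completers-and-compliers set is conventional. That is true, but it does not justify discarding the endpoint event itself when the adjacent intention-to-treat definition already names treatment failure as a cause of early termination.

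**Conclusion.** The point holds as a minor flaw of definition. Section 3.2 removes participants who leave for lack of efficacy, or who are withdrawn for self-treatment after a confirmed infestation, although each is a failure of the kind the trial counts. The consequence is confined to item 4 of section 3.3.

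At leaving rates in line with the protocol's expectation, the effect is negligible: a fall of about 0.01 in each arm's mean proportion and power almost unchanged. It becomes visible only when leaving is common and unequal between arms, and the documents do not fix its direction. All sizes rest on assumed leaving shares and an assumed household size of 4; those in the step 4 table also rest on an unstratified test.

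**What to change.** Add two sentences to section 3.2.

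1. A participant whose infestation is confirmed before Day 14, or who withdraws for lack of efficacy, stays in the per-protocol set and counts as infested, provided the participant was compliant up to that day.
2. Per-protocol membership is applied by household, and a retained household keeps all its participants in the denominator. This also gives the non-compliant households of section 3.4 the definition they now lack.

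The cost is small. No new data are needed, because the diaries record shampoo use and the CRF records failures and withdrawals. Nothing changes in treatment or follow-up. There are two drawbacks: per-protocol rates will look slightly less favourable, and compliance is judged over a shorter window for early failures than for everyone else, so membership is not wholly free of the outcome.
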